In 2012, the estimated number of FSW and distribution FSW by “direct” (i.e., brothel-based) and “indirect” status is presented in Tabel-2. In 2016, the estimated number of FSW was not grouped into direct and indirect because it was considered that most of FSWs had shifted to becoming indirect due to Indonesia’s national policy to close brothels. Due to this policy, most FSWs have become hidden and hard to reach, thus increasing the challenge of increasing HIV testing uptake among this sub-population. Many commercial sex transactions have become underground, especially given the new popularity of digital platforms to sell sexual services. This phenomenon has created a new demand to identify alternative strategies for increasing HIV testing uptake among FSW.

Table 1. Estimated number of female sex workers (2016)

No	Province	Female Sex Workers		
		Point Estimate	Lower Estimate	Upper Estimate
1	Aceh	2,710	583	7,570
2	Sumatera Utara	14,234	8,079	21,943
3	Sumatera Barat	12,783	8,901	17,797
4	Riau	7,181	4,569	9,796
5	Jambi	4,544	1,986	7,188
6	Sumatera Selatan	7,630	4,235	11,323
7	Bengkulu	1,304	566	3,255
8	Lampung	7,532	4,534	10,717
9	Kep. Bangka Belitung	3,313	1,072	5,645
10	Kep. Riau	4,705	3,273	6,664
11	DKI Jakarta	21,405	17,444	25,386
12	Jawa Barat	25,281	17,806	34,220
13	Jawa Tengah	8,938	3,566	18,599
14	DI Yogyakarta	3,511	1,356	6,181
15	Jawa Timur	12,672	6,244	24,661
16	Banten	5,476	3,552	8,012
17	Bali	5,188	3,431	6,955
18	Nusa Tenggara Barat	2,127	1,131	3,212
19	Nusa Tenggara Timur	1,470	141	3,998
20	Kalimantan Barat	11,593	6,231	17,316
21	Kalimantan Tengah	5,208	1,580	11,181
22	Kalimantan Selatan	9,148	4,559	14,662
23	Kalimantan Timur	14,034	8,879	19,459
24	Kalimantan Utara	2,219	1,243	4,128
25	Sulawesi Utara	3,059	898	7,275
26	Sulawesi Tengah	6,052	1,663	10,801
27	Sulawesi Selatan	15,303	7,711	23,144
28	Sulawesi Tenggara	2,058	642	5,400
29	Gorontalo	746	111	2,722
30	Sulawesi Barat	1,376	250	3,076
31	Maluku	1,741	846	3,550
32	Maluku Utara	155	0	1,367
33	Papua Barat	542	326	1,780
34	Papua	1,553	706	5,330
	NATIONAL	226,791	128,114	364,313

Source: Ministry of Health (2016)

Table 2. Estimated number of direct (brothel) and indirect female sex workers (2012)

No	Province	Direct FSW	Indirect FSW
1	Aceh	2,179	929
2	Sumatera Utara	9,032	5,116
3	Sumatera Barat	3,089	2,197
4	Riau	3,643	2,758
5	Jambi	3,937	1,641
6	Sumatera Selatan	3,740	1,719
7	Bengkulu	1,235	1,403
8	Lampung	1,172	845
9	Kep. Bangka Belitung	481	472
10	Kep. Riau	1,195	1,312

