The study will produce scientifically strong evidence as to whether two alternative models of community HIV screening among FSW (assisted and unassisted) result in (1) increased rates of formal HIV testing at health facilities and (2) increased rates of treatment initiation in districts in which the community screening intervention is added to the existing FSW community outreach model.

Two alternative study protocols are described in this document. The bulk of this document presents a protocol for a community randomized controlled trial (cRCT), which is the preferred research design option. However, due to a delay in procurement of the OraQuick® rapid HIV test kits that are to be used in the study, there may be insufficient time to undertake a full cRCT.¹ Accordingly, a contingency protocol that can be implemented in a shorter period of time is also presented.

6. Study Objectives

The primary objectives of this study will provide answers to the following five (5) questions:

1. Does the proportion of FSW who know their HIV status increased?

¹ All research activities must be completed by 31 December 2020.

2. Does the introduction of community HIV screening among FSW increase the rate of HIV testing at health facilities?
3. Does “assisted” or “unassisted” community HIV screening among FSW result in a larger increase in the rate of HIV testing at health facilities?
4. Does “assisted” and “unassisted” community HIV screening among FSW results in a larger increase in the rate of HIV positive case finding?
5. Does the introduction of community HIV screening among FSW increase the rate of initiation of ART?

The secondary objectives of this study will provide answers to the following two (2) questions:

1. What is the acceptability of community-based self-screening for FSWs participating in this study?
2. What is the satisfaction of FSWs participating in this study towards delivery of community-based self-screening?

B. STUDY DESIGN

1. Design Summary

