A Community Randomized Controlled Trial (cRCT) will be used for this study to explore in the HIVST evidence for FSWs in Indonesia with tests and treatment results in intervention acceleration districts compared to control districts with the current standard of care. In the trial, it is recommended the candidates will be tested using two approaches (assisted and unassisted), the latter via direct, fixed and other means of distribution system. A direct distribution system is where and FSW participant is directly given and HIVST by a peer, and a fixed distribution system is where the FSW participant collects the HIVST from a fixed point such as health clinic. Other distribution system may be implemented using courier services such as GO-JEK, etc. This trial aims to determine the acceptability, effectiveness and safety of these HIVST delivery approaches compared with standard of care for improving HIV testing coverage and knowledge of HIV status.

The study will be undertaken in the 23 “acceleration” districts in the National AIDs Program. These are: Kota Medan, Deli Serdang, Kota Palembang, Kota Bandar Lampung, Kota Tangerang Selatan, Tangerang, Kota Jakarta Selatan, Kota Jakarta Timur, Kota Jakarta Pusat, Kota Jakarta Barat, Kota Jakarta Utara, Bogor, Kota Bekasi, Kota Bandung, Kota Depok, Kota Semarang, Kota Surakarta, Kota Malang, Kota Surabaya, Kota Denpasar, Kota Makassar, Kota Sorong and Kota Jayapura. These are districts with high HIV prevalence among HIV key populations, including FSW, and have comprehensive ongoing HIV-TB intervention packages consisting of both health services and community prevention and support programs. As for the FSWs program, these 23 priority districts already implementing a comprehensive outreach package (reach to test and simplified case management for FSWs living with HIV). Table 3 below shows Global Fund targets for FSW HIV testing in 23 priority districts for 2019-2020. Table 4 shows achieved target of HIV testing per semester in 2018-2019 and estimated numbers of direct and indirect FSW in 2012 (MoH, 2013). Table 5 shows achieved target of outreach per year in 2018-2019 in 23 priority districts.

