In the event that participants' data are collected by paper, a procedure to upload the data into the established online system will be developed. Each data manager in the IUs needs to conduct the procedure regularly. This is to ensure that all data are being captured thoroughly.

F. DATA ANALYSES

The data analyses to be undertaken will be directed to addressing the research questions laid out at the beginning of the protocol and statistical tests appropriate to each specific analysis will be performed to inform the interpretation of results. The specific steps in the data analysis will be as follows:

1. Compare the characteristics of FSWs who receive self-testing and blood testing.

2. Compare the characteristics of FSWs who receive assisted and unassisted self-testing.
3. Compare proportion of FSWs taking confirmatory test out of those who receive the test in the assisted and unassisted self-testing.
4. Compare the proportion of FSWs who receive HIV test out of those who got offered for the test (including self-testing) in the intervention group with proportion of FSWs who receive HIV test in the control group.
5. Compare the proportion of FSWs taking confirmatory test (including self-testing) out of those receive the test in intervention groups and control group.
6. Compare the proportion of HIV positive in the assisted, unassisted (intervention) and HIV positive in the control group.
7. Compare the proportion of ART initiation in the assisted, unassisted (intervention) and the control group.
8. Calculate the cascade of HIV testing and treatment.
9. Compare stigma scores and FSWs who went to a health facility for HIV testing between assisted, unassisted group.
10. Compare the HIV and STI risk behaviors between assisted and unassisted group.

G. CONTINGENCY STUDY DESIGN

Should the OraQuick® test kits not become available in sufficient time to conduct a full-scale cRCT, a smaller-scale study will instead be undertaken. The purpose of the smaller study is the same as the cRCT described above, and the same protocol described above will be implemented. But the comparison is achieved targets between before and after intervention – there will be no comparison districts. The study will be undertaken in three (3) districts. The three districts will be selected from different parts of Indonesia, and they are: Kota Bandung (west part of Indonesia), Kota Denpasar (central part of Indonesia), and Kota Makassar (center-east part of Indonesia).

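### The aim is HIV testing coverage, but the only any-test comparison between arms is conditional on being offered a test, so it cannot see a change in how many women are reached

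*Combined protocol and SAP*

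**What the plan says.** Section B.1 (Design Summary) sets the aim as the acceptability, effectiveness and safety of the delivery approaches "compared with standard of care for improving HIV testing coverage and knowledge of HIV status". The first primary objective in Section A.6 is also about FSW in general: "Does the proportion of FSW who know their HIV status increased". Section A.1 gives the reason for new routes, saying that "most FSWs have become hidden and hard to reach".

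Section F, item 4, reads: "Compare the proportion of FSWs who receive HIV test out of those who got offered for the test (including self-testing) in the intervention group", to be set against the control arm "with proportion of FSWs who receive HIV test in the control group". The offered denominator is explicit for the intervention arm only.

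Sections C.1 and C.3 add a route that exists only in intervention districts: broadcast messages, an online link and courier delivery, with no outreach contact needed. Section E.3 records numbers contacted and offered in both arms. For the unassisted approach it also records link accesses, eligible women and baseline completions.

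**The concern.** Coverage is reach multiplied by uptake: women offered out of those eligible, times women tested out of those offered. Item 4 contains only the second factor. The online route is meant to bring in women whom outreach does not contact. Those women enter the denominator once they are offered a test, so the denominator is shaped by the intervention after randomisation, and in one arm only.

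No other item fills the gap:
- Item 5 is conditional on having received a test.
- Items 6 and 7 concern positivity and ART and state no denominator.
- Item 8 is a cascade with no stated starting point and no comparison.
- The SIHA data in Section B.5 are proposed for the positive-case and treatment question.
- The comparison of achieved targets in Section G applies only if the cRCT is not run.

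At stake is the headline conclusion. A reader could take item 4 as the effect on coverage when it is the effect on uptake in a changing group.

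**Working it through.** **The plan's own figures.** No planned figure concerns any-test coverage. The sample size of 635 per group (423 × 1.5 = 634.5 at one-sided 5% and 90% power) is for facility testing, 50% against 60%. I use it only as the source of a 50% starting uptake and a 10-point effect.

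**Inputs.** Summing Tables 4 and 5 by the Table 6 allocation:
- Tests per semester: 6,433 (15 intervention districts) and 3,342 (8 comparison districts).
- Outreach contacts per year: 36,979 and 15,993.
- Annualised tests over contacts, intervention districts: 2 × 6,433 / 36,979 = 34.8%. This is a programme ratio, used as a second starting value. Across the 23 districts it runs from 0.17 to 0.68.

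Assumptions not in the documents: the online route adds a = 20% more women; uptake q among them is 15–30% (start 34.8%) or 20–40% (start 50%).

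**Formulas.** Let p be the starting uptake and p′ the uptake among existing clients during the trial.
- Item 4 proportion = (p′ + a·q) / (1 + a)
- Ratio of women tested = (p′ + a·q) / p = (1 + a) × (item 4 proportion / p)

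The last equality is the point: women tested change by the item 4 ratio times the reach ratio, and item 4 does not see the reach ratio.

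| p | p′ | q | Item 4 proportion | Change in item 4 | Women tested |
|---|---|---|---|---|---|
| 50% | 60% | 20% | 0.64/1.2 = 53.3% | +3.3 | +28% |
| 50% | 60% | 40% | 0.68/1.2 = 56.7% | +6.7 | +36% |
| 34.8% | 44.8% | 15% | 0.478/1.2 = 39.8% | +5.0 | +37% |
| 34.8% | 44.8% | 30% | 0.508/1.2 = 42.3% | +7.5 | +46% |
| 50% | 50% | 20% | 0.54/1.2 = 45.0% | −5.0 | +8% |
| 50% | 50% | 40% | 0.58/1.2 = 48.3% | −1.7 | +16% |
| 34.8% | 34.8% | 15% | 0.378/1.2 = 31.5% | −3.3 | +9% |
| 34.8% | 34.8% | 30% | 0.408/1.2 = 34.0% | −0.8 | +17% |

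If added women test more readily (p = p′ = 50%, q = 60%), item 4 is 0.62/1.2 = 51.7%, up 1.7 points, while women tested rise 24%.

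**When the sign flips between arms.** At 50% control and 40% intervention uptake, coverage still favours intervention if its reach exceeds 0.5/0.4 = 1.25 times control reach. At 50% and 60%, coverage favours control if intervention reach is below 0.5/0.6 = 0.83 of control reach. Per 1,000 eligible women, with 400 offered and 50% tested in control (coverage 20%), 600 offered and 50% tested gives coverage 30%: a gain of 10 points where item 4 shows 0.

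**Precision of a district comparison.** Seven randomisation groups are 2:1 and one is 1:1. With SD s of district log ratios, the combined SE is s/√(7/1.5 + 1/2) = 0.44s, on 23 − 8 − 1 = 14 degrees of freedom. The ratio detectable with 80% power (two-sided 5%) is exp[(2.145 + 0.868) × 0.44s]: 1.30, 1.49 or 1.94 for assumed s of 0.2, 0.3 or 0.5.

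**The case against.** The strongest reply is that reversal depends on the assumptions. Kits go to women who decline a facility test, and item 4 counts self-tests, so uptake among existing clients should rise. With the plan's own 10 points, item 4 still moves in the right direction. Women who order a kit online are also self-selected, so low uptake among them is not obvious. This stands: reversal is a limiting case, and what remains in the favourable case is understatement.

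A reader might infer several stronger points that the documents do not support:
- That the plan will report harm while testing rises. This needs little change in existing clients together with clearly lower uptake in added women.
- That 34.8% is pre-trial uptake. Section C.4 counts one test per woman per six months, so doubling can count a woman twice, and Table 5 is not limited to women eligible for the trial.
- That outreach will shrink as peer workers turn to kits. Section C.1 describes screening as an addition, and no figure suggests a fall.
- That reach goes unrecorded. Section E.3 records contacted and offered counts in both arms; they are missing from the planned comparison, not from the data.
- That missing or outdated population sizes undermine the analysis. Section B.1 says that "Table 4 shows achieved target of HIV testing per semester in 2018-2019 and estimated numbers of direct and indirect FSW in 2012", while the printed table holds only test counts. That may be a cross-reference slip or a loss in text extraction, since Table 2 gives the 2012 sizes by province. No planned analysis divides by them.

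The limited power of a district comparison is also a fair objection, and it constrains the remedy.

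**Conclusion.** The mismatch between aim and analysis is real. Item 4 answers a legitimate question, uptake among women offered, but not the coverage question in Section B.1 or the knowledge-of-status question in Section A.6. With 20% more women reached, it shows a relative gain of about 7% to 22% (0.533/0.500 to 0.423/0.348) where women tested rise 28% to 46%. In the less favourable case it falls 0.8 to 5.0 points while women tested rise 8% to 17%. All of these figures rest on assumed reach and assumed uptake among added women, and on online women counting as offered, which the plan does not define. The unstated control denominator is a second, separate ambiguity: if it is not women offered, the two arms are not measured alike.

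**What to change.** 1. Label item 4 as uptake among women offered a test. Use the same offered denominator in both arms, and state at which step an online woman counts as offered (for example link access, eligibility or baseline completion). Do not draw the coverage conclusion from item 4 alone.
2. Add a district-level comparison of FSW tested during the intervention period: all routes first, then facility tests only. Use the Table 4 count definition (one test per woman per semester) from the same Implementing Unit source before and during the trial, with one calendar window for all 23 districts. Adjust for the Table 4 baseline and the eight randomisation groups.
3. Report contacted and offered counts by arm beside it.
4. Describe the result as change in the number of FSW tested relative to baseline. It has no population denominator, so it is not coverage and should not alone carry a coverage claim.

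The cost is SAP wording and one analysis built on counts that the Implementing Units already report, with self-tests added under the one-per-woman rule. De-duplication in comparison districts would rest on the programme's own rule, because the study's temporary IDs are described for study participants. The main downside is precision: even gains of 28% to 46% could be missed unless district log ratios vary little, and gains of 8% to 17% probably would be. The interval should be reported, and a non-significant result should not be read as no effect.

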The flowchart of the study is presented in Figure 1. Randomization was carried out among the 23 priority districts in this study with a ratio of 2:1 (that is, 2 intervention districts per 1 control district). The details of randomization are explained in section B.4 of this document. **The assigned 15 intervention districts and 8 comparison districts** are described in Table 6. Potential participants in the intervention area will be screened through the inclusion and exclusion criteria established for

this study. The criteria for participants who are eligible for this study are explained in section B.3 of this document and Annex2.

According to the Indonesian Ministry of Health's current recommendation, HIV blood test at an authorized health facility is still the current practice for HIV diagnosis. Both participants in the intervention and comparison area will be offered for HIV blood test at a health facility. Participants in comparison areas and participants in intervention areas who agree to take HIV test at a health facility will then be managed further according to the existing guideline or "standard of care." For participants in intervention areas who refuses to have her blood drawn for HIV test at a health facility will then be offered self-testing using OraQuick®. Participants will then fill and sign the informed consent to participate in CBS study.

Next, participants will be offered to do the test assisted or unassisted. If the participant chooses to perform the test assisted, the PL/PE will help her from filling in a baseline survey, performing the test, and filling in a post-test survey. If the participant chooses to perform the test unassisted, there will be two options for the participant to get the test kit. First, PL/PE will deliver the test kit for the participant, help with filling in the baseline survey on the spot and give information about uploading test results and the post-test survey, along with a hotline number to call for any questions and concerns, including follow-up steps after participants have received the results. The second method, participants will be given a link online which will entitle information of this study, eligibility criteria, informed consent, baseline survey, link to order a test kit, link to upload result and link to fill in the post-test survey. Participant who chooses this second method will also be given hotline number should there be any further inquiries.

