3.1 Study kick-off										
3.2 Data collection										
4. Data analysis and report writing										
5. Workshop for study finding dissemination										

3. Eligibility Criteria

The target audience for the intervention to be evaluated are FSW in Intervention districts that meet the criteria outlined below.

Inclusion criteria

- Women, 18 years or older at enrolment
- Reports transactional sex (vaginal, oral and/or anal) at least once in the past month
- No HIV test in last 6 months
- Self-reported HIV negative OR HIV status unknown

Exclusion criteria

- Unwilling to participate for any reason
- Concurrently participating in another HIV prevention study

4. Randomization

Stratified randomization was carried out for the 23 priority districts involved in this study. First, sampling strata were created by sorting the mean average value of achieved HIV testing target per semester from 2018-2019 in each district from the largest to the smallest. The second step was to sort the districts into eight groups of three districts, except for the last group which will only consist of two districts. Randomization for intervention and comparison group were then carried out within these groups of eight with 2:1 ratio (2 intervention: 1 comparison).² The results of stratified randomization are presented in Table 6. In separate table, Table 7 contains 15 intervention districts and Table 8 contains 8 comparison districts.

² A 2-to-1 intervention to comparison district ratio was chosen in order to increase the likelihood of recruiting a sufficient number of FSW for community screening to reach the sample size target considering the relatively short time frame available for for study implementation.

Table 6. Allocated intervention group and comparison group

No	Kab/Kota	Region	Achieved target of HIV testing per semester (2018-2019)	Group
1	Kota Denpasar	3	982	Intervention
2	Kota Makassar	3	866	Comparison
3	Kota Palembang	1	694	Intervention
4	Kota Jakarta Utara	1	612	Comparison
5	Kota Medan	1	575	Intervention
6	Kota Surabaya	3	568	Intervention
7	Kota Jakarta Barat	1	544	Intervention
8	Kota Bandung	2	487	Comparison
9	Kota Jakarta Timur	1	479	Intervention
10	Kota Jakarta Pusat	1	473	Intervention
11	Kota Jakarta Selatan	1	448	Comparison
12	Kota Sorong	4	415	Intervention
13	Kab. Tangerang	1	391	Intervention
14	Kota Bogor	2	374	Intervention
15	Kota Jayapura	4	323	Comparison
16	Kota Bandar Lampung	1	319	Comparison
17	Kota Depok	2	287	Intervention

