Sample size requirements for the third question measurement pertains to the number of FSW who test positive for HIV at a health facility and are thus eligible to initiate treatment. This will depend upon (1) the number of FSW presenting at health facilities for testing and (2) the positivity rate among those tested. Sample sizes should thus be calculated accordingly. If we assume a testing positivity rate of 3%, it is apparent that the expected number of FSWs who would be eligible for treatment will be small and we will lack sufficient statistical power to make meaningful comparisons with comparison districts. For this reason, it is recommended that the impact of community screening among FSW be measured using SIHA data for FSW in both intervention and comparison districts. This estimate of impact derived in this way will be confounded if it were to be the case that interventions other than HIV self-testing were to be better implemented in intervention vs. comparison districts. It might be possible to minimize this potential bias by including measures of intervention implementation performance in the intervention and comparison districts in multivariable analyses. Thus, a large enough sample size is required to ensure sufficient power to determine the difference in the intervention and control districts.

C. THE INTERVENTION

1. General Description of The Intervention

FSW who meet the eligibility criteria will be offered for HIV blood test first. Participants who wish to take the test will then managed according to the current guideline for standard of care. Participants who disagree to take HIV blood test will then be offered screening test with Ora-Quick®. There will be with two options for community HIV screening by Peer Leaders: (1) in a convenient community setting assisted by PL/PE (assisted screening) or (2) in a setting of their own choosing without assistance from PL/PE (unassisted screening). FSW will also be able to access a community-based screening test by following online link from messages spread through WhatsApp number without having to come into contact with outreach workers. The saliva-based Ora-Quick® test kit will be used for community screening.

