- How likely is it that the client will get a HIV test at a health facility as a result of the community screening test, on a scale of 1-5
- Comments and suggestions.

3. Routine Recording

Because of limitations in the data recorded and reported by health facilities, the study will rely primarily upon data recorded by IU outreach staff. Modifications will be made to the data recording and reporting systems currently being used to facilitate collection of the data needed for the study in a manner that minimizes additional recording and reporting burden. The nature of the adjustments to be made will be different for "assisted" and "unassisted" community screening.

To capture the data needed for of this study, the following data need to be recorded:

No	Data Recorded	Intervention Group	Control Group
1	Number of FSW contacted via outreach that were at least 6 months since their last HIV test for whom testing at a health facility was recommended	Yes	Yes
2	Numbers of FSW offered for HIV test at health facility	Yes	Yes
3	Numbers agreeing and disagreeing to testing at a health facility	Yes	Yes
4	Of those agreeing to getting tested at a health facility, the numbers that actually went to a health facility and were tested for HIV	Yes	Yes
5	Number of FSW offered for OFT screening	Yes	No
6	Among FSW not agreeing to be tested at a health facility, the numbers that agreed to (1) assisted community HIV screening and (2) unassisted community HIV screening	Yes	No
7	Numbers that were actually screened, assisted and unassisted	Yes	No
8	The number of community screening tests that were reactive	Yes	No
9	Among FSW with reactive community screening tests, the numbers that were subsequently tested at a health facility	Yes	No
10	Number of FSW initiating ART	Yes	Yes

For **unassisted** approach, additional information will be gathered as indicated below:

1. Numbers of FSW who access the link online
2. Numbers of FSW who are deemed eligible
3. Numbers of FSW who fill in baseline survey and agree to participate
4. Numbers of FSW who agree to take HIV test at health facility
5. Numbers of FSW who request the kit being delivered vs picking-up at fixed location
6. Numbers of FSW who upload the test result
7. Numbers of reactive vs non-reactive test result
8. Numbers of FSW who complete the post-test survey

9. Among FSW with community screening tests, the numbers that were subsequently tested at a health facility (reactive OR non-reactive)
10. Number of FSW initiating ART

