Annex 1. Flowchart of Routine Data Recording

Annex 2. Eligibility Form

Eligibility Participants Form for Intervention

To be completed by PL/PE during FSW outreach

These checklists are to be completed by PL/PE during FSW outreach to assess the eligibility of FSW to participate in this study. If questions number 1-7 is answered “Yes”, then participant is eligible for the study. If question number 8 is answered “Yes”, then participant is not eligible for the study, but eligible for “blood test study in health facility”.

No	Criteria inclusion	Yes	No
1	Female, aged 18 years old or more		
2	Admit having transactional sex (vaginal, oral, or anal) at least once within the last one month		
3	Have never had any HIV test taken within the last 6 months		
4	Self-reported HIV Negative OR HIV status unknown		
5	Agreed to participate in this study		
6	Not currently participating in any other HIV prevention study		
7	After being offered for HIV testing in health facility, participant stated: A. Agree for HIV testing in health facility* B. Not agree for HIV testing in health facility**		

Note:

* Use information form for VCT

** Use information form for OFT

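### Apart from the six-month testing gap, eligibility is defined only for intervention districts and analysis 4 states no control denominator, so the main testing comparison may count differently selected women in the two arms

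*Combined protocol and SAP*

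**What the plan says.** **Who is screened.** B.1 (Design Summary) states: "Potential participants in the intervention area will be screened through the inclusion and exclusion criteria established for" this study. B.3 (Eligibility Criteria) opens with "The target audience for the intervention to be evaluated are FSW in Intervention districts that meet the criteria outlined below". The criteria are female sex and age 18 or over, transactional sex in the past month, "No HIV test in last 6 months", and "Self-reported HIV negative OR HIV status unknown". The exclusions are "Unwilling to participate for any reason" and current enrolment in another HIV prevention study. The Annex 2 checklist is headed "Eligibility Participants Form for Intervention".

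**When the criteria apply.** C.1 says "FSW who meet the eligibility criteria will be offered for HIV blood test first". In Annex 2, agreement to take part is item 5 and the woman's answer to the facility-test offer is item 7.

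**Comparison districts.** B.5 and C.4 leave them on the standard programme, and no eligibility or consent step is described. E.3 marks rows 1 to 4 for both groups. Row 1, which is limited to women who were advised to test, begins "Number of FSW contacted via outreach that were at least 6 months since their last HIV test for whom testing at a health facility was". Rows 2 to 4 count women offered, agreeing or refusing, and actually tested.

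**Analysis.** In section F, item 4 compares the proportion tested, self-tests included. The intervention denominator is women offered a test. The control denominator is not stated.

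**The concern.** Randomising districts protects the comparison only if the same kind of woman is counted in both arms. A filter applied after allocation, in one arm, undoes that protection. Willingness matters most, because women who want nothing to do with a testing study are likely to be those least likely to test. If they leave the intervention denominator but stay in the comparison denominator as refusals, the intervention rate rises with no effect at all.

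Analysis 4 is the main between-arm comparison of testing uptake. Later adjustment would not be enough if comparison districts never record age, recent transactional sex and self-reported status at contact.

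**Working it through.** **1. The plan's own figures (B.5).** P1 = 0.50 (comparison), P2 = 0.60 (intervention), design effect 1.5, 635 per group, 761 after a 20% allowance. With the mean proportion 0.55 and Z = 1.645:

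n = [1.645 × √(2 × 0.55 × 0.45) + 1.282 × √(0.25 + 0.24)]² / 0.10² = 422.2, taken as 423; 423 × 1.5 = 634.5; 634.5 × 1.2 = 761.4.

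This matches 635 and 761. The printed Z = 1.96 gives 519 × 1.5 = 778.5, which does not match. That mismatch is a separate matter. The yardstick needed here is the 10-point planned effect at a 50% base rate.

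**2. Which criteria reach which arm.**

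| Criterion | Intervention (B.3, Annex 2) | Comparison (E.3, C.4) |
|---|---|---|
| No test in 6 months | yes | yes, row 1 |
| Age 18 or over | yes | not stated |
| Transactional sex, past month | yes | not stated |
| Self-reported negative or unknown | yes | not stated; row 1 also requires that testing was recommended |
| Not in another HIV prevention study | yes | not stated |
| Willing to take part | yes | not stated |

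**3. When willingness applies.** C.1 and the order of the Annex 2 items put it before the facility-test offer. The extra records for the unassisted route in E.3 run the same way: eligible, then agreed to participate, then agreed to a facility test. Against this, B.1 places signed consent after the facility test has been refused and self-testing offered. C.2(a) recommends testing on the six-month rule alone. The two sets of passages give different counts of women offered a test.

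**4. Illustration on the C.1/Annex 2 reading.** Assumptions, none of them given in the documents: no true effect; 50% of all contacted women test in both arms; a share w is unwilling; a proportion t of the unwilling would test. The comparison rate stays at 0.50. The intervention rate is

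(0.50 − w × t) / (1 − w).

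For w = 0.20 and t = 0.10: (0.50 − 0.02) / 0.80 = 0.600.

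| w | t = 0 | t = 0.10 | t = 0.25 |
|---|---|---|---|
| 0.10 | 0.556 (+5.6) | 0.544 (+4.4) | 0.528 (+2.8) |
| 0.20 | 0.625 (+12.5) | 0.600 (+10.0) | 0.562 (+6.2) |
| 0.30 | 0.714 (+21.4) | 0.671 (+17.1) | 0.607 (+10.7) |

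Differences are in percentage points. If t = 0.50 the bias is zero, so the direction depends on unwilling women testing less than the others. With t = 0, a share of 1 − 0.50/0.60 = 16.7% produces the whole 10 points.

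**5. Consequence for the test.** Effective size per group is 635 / 1.5 = 423. With no true effect, the chance that a two-sided 5% test favours the intervention is 37% (w = 0.10) and 96% (w = 0.20) if t = 0. It is 13% and 45% if t = 0.25.

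**The case against.** **Refusers may already be counted.** C.2(a) to (c) start from the six-month rule and keep women who refuse facility testing or self-screening in the process. E.3 row 3 counts refusals in both arms. A reader might infer that unwilling women are certainly dropped in intervention districts. The documents do not establish that, because the passages disagree. What stands is that district teams could count either way, and section F does not commit to rows 1 to 4 as the denominator.

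**Known HIV-positive women.** It is tempting to say they pull down the comparison rate as untested women. Row 1 is limited to women for whom testing was recommended, and B.1 says all 23 districts already run case management for women living with HIV. Row 1 may therefore drop them already. No figure is justified.

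**Other outcomes.** A reader might infer that analyses 6 and 7 also favour the intervention. Analysis 6 states no denominator. If it is women tested, known positives who were retested in comparison districts would raise positivity there, against the intervention. For analysis 7, B.5 points the treatment question to SIHA data from both groups of districts, and E.3 row 10 carries no eligibility limit. For facility testing alone, B.5 describes the intervention sample as self-testers, who under C.1 have declined the facility test. That selection runs the other way.

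**The missing rule may be elsewhere.** B.1 mentions participants in comparison areas, and B.5 mentions recruiting 761 women there. Figure 1 and the Annex 1 flowchart could not be read in the text available and might show a comparison pathway. E.1 does not limit the baseline survey to one arm, and the questionnaire asks age and recent clients. It does not ask self-reported HIV status, however, and is addressed to women who have agreed to take part. None of this supplies a common denominator in the text.

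**Conclusion.** The point holds for analysis 4. Apart from the six-month gap, the criteria are specified for intervention districts only, the text conflicts on whether willingness comes before or after the facility-test offer, and the control denominator is missing. If C.1 and Annex 2 are followed, the comparison involves differently selected women and tends to favour the intervention.

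The size cannot be derived from the documents. The range of about +4 to +17 points assumes 10% to 30% unwilling, 10% of them testing, a 50% base rate and no true effect. It shows only that moderate shares could produce a difference as large as the planned 10 points. If willingness is applied after the offer and refusals are counted in both arms, this component disappears. The other one-sided criteria remain.

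Analyses 6 and 7 lose comparability under the same one-sided rule, with no established direction. This should be settled before data collection, because it affects the main testing comparison and the missing comparison-arm items may not be recoverable afterwards.

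**What to change.** - **Denominator (B.3, section F).** Define one for both arms: women contacted by outreach who meet Annex 2 items 1 to 4 (age, transactional sex in the past month, no test in six months, self-reported negative or unknown status), counted before consent. Name it in analysis 4 for both groups.
- **Recording (E.3, Annex 2).** Have outreach staff in the 8 comparison districts complete items 1 to 4 at contact. Restrict E.3 rows 1 to 4 to those women in both arms. Retitle the form so that it covers both groups.
- **Willingness.** Keep item 5 and the first exclusion criterion only as conditions for self-screening and the surveys. Women who decline stay in the denominator as offered, not tested. Item 6 (another HIV prevention study) can be handled the same way.
- **Consistency.** Reconcile C.1 and Annex 2 with B.1 and C.2 on when willingness applies.

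The cost is wording in these sections and four checklist items for staff who already record rows 1 to 4. No extra participants or staff are needed. The downside is slightly more recording in comparison districts and possibly a lower intervention testing rate. The ethics submission should cover recording these items before consent.
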